6 STUDY DESIGN

6.1 Overview of Study Design

This is a post-market, multicenter, non-comparative, open-label, prospective clinical study.

The study will be conducted outside the US, where the Systane Ultra PF is commercially available, in clinical sites known to routinely manage subjects with DED and CL wearers. The overall study duration (first subject screened to last subject's final study visit) is expected to be approximately 2 months.

Subjects will be enrolled into the study after signing the informed consent form (ICF).

Subjects who meet all the inclusion criteria and none of the exclusion criteria will initiate treatment with Systane Ultra PF. Eligible study participants (Group 1 and Group 2) will receive the first dose of Systane Ultra PF at the Screening/Baseline visit and will be required to self-administer Systane Ultra PF four times daily up to Visit 3. The dose selected in this study is the dose approved for Systane Ultra PF for the management of DED.

[figure not shown]
Subjects will participate in the study for approximately 30 days, with a phone call scheduled on Day 15 ± 2 (Visit 2) and a follow-up visit scheduled on Day 30 ± 2 (Visit 3). Subjects may have unscheduled visits if deemed necessary per the Investigator's judgment.

Subjects will be asked to complete patient questionnaires on Day 1 and at Visit 3 (Impact of Dry Eye on Everyday Life - Symptom Bother [IDEEL-SB] or Contact Lens Dry Eye Questionnaire [CLDEQ-8] and Comfortable Wear Time questions). In addition, the subjects will be instructed to document Systane Ultra PF dosing information on a daily basis using a subject diary.

A summary of the study design is shown in Figure 1. Study assessments are shown in the Schedule of Assessments (Table 4).

The study will enroll 68 subjects with the objective of 54 subjects completing treatment (27 in Group 1 and 27 in Group 2).

Figure 1. Overall Study Design

CL: Contact lens; QID: Four times a day.

Systane Ultra Preservative-free will be dispensed at Screening/Baseline visit. Subjects will be expected to attend one additional visit at Day 30 (± 2 days) after screening and a telephone call visit at Day 15 (± 2 days).

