6.4.3 Prior and Concomitant Therapy or Medications

Concomitant Medications

Targeted concomitant medications (see Section 7.3.2) must be recorded in source documents and on the appropriate electronic case report form (eCRF).

Prohibited Concomitant Medications

For subjects who meet all of the inclusion criteria and none of the exclusion criteria, the initiation

of systemic medications known to cause dry eye (e.g., anti-histamine, anti-depressants, anti-psychotics, benzodiazepines, etc.) or known to treat dry eye (e.g., Restasis, Xiidra, Cequa) is not permitted during the study.

Rescue Medicine

Not applicable.

6.4.4 *Inclusion Criteria*

Subjects will be eligible to participate in the study if **all** of the following conditions exist:

1. Subject must be at least 18 years of age.
2. Subject must be able to understand and sign an IRB/IEC approved informed consent form.
3. Subject must be willing and able to attend all study visits as required per protocol.
4. Subject with mild to moderate dry eye (IDEEL-SB >16-64).^a
5. Subject with CL-related dry eye symptoms (CLDEQ-8 ≥12).^b
6. Subject with a comfortable wear time with habitual contact lenses, which is less than the total wear time by at least 3 hours.^b
7. Subject must be willing to discontinue use of all habitual artificial tear supplements and use only the study device as directed for the entire study duration.
8. Subject using cyclosporine or other topical dry eye medications must be on a stable dosing regimen for ≥60 days prior to enrollment.

^a Assessed in Group 1 only (subjects with mild to moderate dry eye)

^b Assessed in Group 2 only (subjects with end of day CL-related dryness)

6.4.5 *Exclusion Criteria*

Subjects will be excluded from participation in the study if any of the following conditions exist:

1. Has suffered any ocular injury to either eye in the past 3 months prior to screening.
2. Has undergone any other ocular surgery (including intraocular surgery) within the past 6 months or has any ocular surgery planned during the study.
3. Employee or family member of Investigators or Alcon.

4. Currently enrolled in any clinical trial.

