5. Use of any systemic medication known to cause dry eye (e.g., anti-histamine, anti-depressants, anti-psychotics, benzodiazepines, etc.) for less than 1 month before the Screening visit. If subject was on a stable regimen for at least a month prior to the Screening visit, the dosing regimen must not have changed for the duration of their participation in this study. In addition, subjects who did not currently use any of these medications could not start a regimen while participating in the study.

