9.7 Anticipated Clinical Benefits and Risks

9.7.1 *Known Potential Risks*

Systane Ultra PF may cause mild eye burning or irritation, itching or redness of the eyes, watery eyes, blurred vision, or unpleasant taste in the mouth. There may be a rare possibility of an allergic reaction, which could be severe.

Systane Ultra PF must be stopped in the event of eye pain, changes in vision, redness or irritation of the eye(s) gets worse, persists or lasts more than 72 hours.

9.7.2 *Known Potential Benefits*

Previous clinical studies showed that Systane Ultra is effective for the temporary relief of burning and irritation due to dryness of the eye.

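### The protocol names a rare, possibly severe allergic reaction as a known risk, but no eligibility criterion deals with known hypersensitivity or a previous reaction to the product

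*Protocol*

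**What the plan says.** Protocol 9.7.1 (Known Potential Risks) lists mild local effects and then adds: "There may be a rare possibility of an allergic reaction, which could be severe".

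Protocol 6.4.5 opens with "Subjects will be excluded from participation in the study if any of the following conditions exist". Its five items, repeated in the synopsis, are in summary:

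1. An eye injury within three months of screening.
2. Eye surgery in the preceding six months, or planned while the study runs.
3. Working for, or being related to, the investigators or the sponsor.
4. Taking part in another trial.
5. "Use of any systemic medication known to cause dry eye", where that use began less than a month before screening, with conditions on keeping the regimen stable during the study.

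Protocol 6.1 turns eligibility into treatment: "Subjects who meet all the inclusion criteria and none of the exclusion criteria will initiate treatment with Systane Ultra PF". It places the first dose at the Screening/Baseline visit. SAP 1.3.2 refers back to the protocol's two lists and adds no criterion.

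**The concern.** The protocol identifies a hazard specific to the product, but its entry rules do not screen for the people in whom that hazard is most foreseeable. Such people could plausibly present. The product is already on sale where the study is run (Protocol 6.1 and Table 1), and inclusion criterion 7 expects some subjects to be habitual users of artificial tears, so earlier exposure is realistic.

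After Visit 1 the subject self-administers four times daily for about 30 days, with one scheduled telephone call before the final visit. What is at stake is an avoidable exposure of a subject to a risk that the protocol itself lists.

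**Working it through.** No figure in the plan bears on this point, so the check is a reading of the passages against each other.

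**Step 1: is the risk stated?** Yes, in Protocol 9.7.1. It is described as rare and as possibly severe. Both qualifiers matter.

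**Step 2: does any exclusion cover it?** The five items concern ocular injury, ocular surgery, a relationship to the investigators or sponsor, enrolment in another trial, and systemic medication that causes dry eye. None mentions allergy, hypersensitivity or intolerance. There is no general exclusion at the investigator's discretion.

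**Step 3: does any inclusion criterion cover it?** The eight items in 6.4.4 concern age, consent, attendance, the IDEEL-SB range, the CLDEQ-8 threshold, comfortable wear time, willingness to stop other tear products, and stable topical dry eye medication. None covers it.

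**Step 4: could the item have been lost in redaction or in reading the PDF?** This is not a plausible explanation. The numbering runs from 1 to 5 in both the synopsis and 6.4.5, and in the body section 6.4.6 follows item 5 directly.

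**Step 5: does another provision act as an entry rule?**

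| Provision | What it does | Acts at entry? |
|---|---|---|
| Protocol 7.3.2 and Table 3 | Records medical history over the previous year, including atopic disease (urticaria and angioedema among the examples) and other ocular history; further questions are at the investigator's discretion | Asked at Visit 1, but with no eligibility consequence; no product-allergy item; an older reaction need not be recorded |
| Protocol 9.7.1, stopping text | Applies to reactions once the product is in use | No |
| Protocol 6.4.6, physician decision | A reason for discontinuing participation | Not an eligibility criterion |
| Protocol 4, instructions for use | Governs handling of the device | No |
| Protocol Table 1, label text | Gives uses, some directions and storage | Shows no contraindication |
| SAP 4.1, disposition | Counts ineligibility under two reasons: an inclusion criterion not met or an exclusion criterion met | Offers no category for a subject declined because of allergy |

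**Step 6: put together.** The subject has a known previous reaction, meets all eight inclusion criteria as they apply to the group, and meets none of the five exclusions. Section 6.1 then leads to treatment at Visit 1. Nothing in either document interrupts that sequence with a written criterion. A site that sensibly declined the subject would have no criterion to cite and no matching disposition category, so sites could handle the same case differently.

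**The case against.** The best reply is that the harm is already unlikely. Consent must cover the known risks (Protocol 13), and a person who knows they reacted to these drops is unlikely to agree to use only them for a month. Atopic history is asked at Visit 1, the investigator may probe further, and section 9.5 makes the investigator responsible for safe care. The sentence in 6.1 describes the flow of the study; it does not oblige anyone to dose a person with a known allergy. The full package insert is not among the documents and may itself warn against such use.

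Much of this stands, and it limits how strongly the point can be put. It does not close the gap: each safeguard depends on individual judgment or on an unseen source, and none is a uniform entry rule.

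Two stronger readings are tempting, and the documents support neither.

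- A reader might infer that the product is likely to cause a severe reaction. Section 9.7.1 says only that a reaction is a rare possibility and that it could be severe.
- A reader might infer that one such reaction would materially distort the reported adverse event rate. At the planning proportion of 0.0543, 54 × 0.0543 = 2.93 subjects would be expected to have an event, so one more looks large. That sum assumes the reaction occurs, and no document says how likely such a subject is to enrol. It also uses the completion target, whereas safety is analysed in everyone dosed: one subject is 1/54 = 1.9 points, but 1/68 = 1.5 points if all 68 recruited are dosed. Ocular events are summarised by eye (SAP 6.3.1), and nothing shows that 0.0543 leaves allergic reactions out. In a descriptive single-arm study a reaction to the product is a genuine adverse event, and reporting it is not bias.

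**Conclusion.** The point holds as an omission in the eligibility rules that should be corrected. A risk named in section 9.7.1 has no counterpart in sections 6.4.4 and 6.4.5 or in the synopsis. Followed literally, the protocol admits a person with a known previous reaction, provided every other criterion is met, and doses that person at the first visit.

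No magnitude is attached. The conclusion rests on the text of the two documents alone and assumes nothing about how often the situation would arise or what the full package insert says. It rests on subject protection, and it leaves the endpoints and planned analyses unaffected.

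**What to change.** The sponsor should reconcile section 9.7.1 with section 6.4.5 and the synopsis, so that known hypersensitivity to the product or its components has an explicit consequence for eligibility. It should be asked about at Visit 1 with the medical history already collected there, without relying on the one-year look-back or on discretionary follow-up questions. The exact criterion and its wording are for the sponsor to decide.

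Once a criterion exists, a subject declined on this ground can be counted in the SAP's existing disposition categories, so the SAP needs no new analysis. The cost is one line in an amendment, one question at Visit 1 and possibly a very few extra screen failures.

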6.4.6 Exit / Discontinuation Criteria

Participation of a subject in this clinical study may be discontinued for any of the following reasons:

- Screen failure
- AE/serious adverse event (SAE)
- Death
- Lack of efficacy
- Lost to follow-up
- Physician decision
- Protocol violation
- Study terminated by Sponsor or regulatory authority
- Technical problems with the study device
- Withdrawal by subject

If a subject withdraws prematurely from the study due to the above criteria or any other reason, study staff should make every effort to complete the full panel of assessments scheduled for the Early Exit Visit. The reason for subject withdrawal must be documented in the eCRF.

In the case of subject lost to follow-up, attempts to contact the subject must be made and documented in the subject's medical records. Withdrawn subjects will not be replaced.

A subject will be considered lost to follow-up if he or she fails to return for scheduled visits and is unable to be contacted by the study site staff. The following actions must be taken if a subject fails to return to the clinic for a required study visit:

- The site will attempt to contact the subject and reschedule the missed visit as soon as possible and counsel the subject on the importance of maintaining the assigned visit schedule and ascertain if the participant wishes to and/or should continue in the study.

- Before a participant is deemed lost to follow-up, the Investigator or designee will make every effort to regain contact with the subject (where possible, 3 telephone calls and, if necessary, a certified letter to the subject's last known mailing address or local equivalent methods). These contact attempts should be documented in the subject's medical record or study file.
- Should the subject continue to be unreachable, he or she will be considered to have withdrawn from the study with a primary reason of lost to follow-up.

7 STUDY PROCEDURES

7.1 Informed Consent

Subjects will be provided a consent form describing this study and providing sufficient information for subjects to make an informed decision about their participation in this study. The Investigator or his/her representative will explain the nature of the study to the subject and answer all questions regarding the study.

Subjects must be informed that their participation is voluntary. Subjects will be required to sign a statement of informed consent that meets the requirements of 21 Code of Federal Regulations (CFR) 50, local regulations, International Conference on Harmonization (ICH) guidelines, Health Insurance Portability and Accountability Act (HIPAA) requirements, where applicable, and the IRB/IEC or study center.

The medical record must include a statement that written informed consent was obtained before the subject was enrolled in the study and the date the written consent was obtained. The authorized person obtaining the informed consent must also sign the ICF.

Subjects must be re-consented to the most current version of the ICF during their participation in the study.

A copy of the ICF must be provided to the subject.

7.2 Vulnerable Populations

Members of vulnerable populations will not be specifically targeted for recruitment. However, the intended subject population may include subjects who are considered to be vulnerable by definition. The procedures included in this protocol are sufficient to provide the necessary human subjects' welfare protections without the need for additional procedures.

7.3 Clinical Procedures and Assessments

After obtaining informed consent, assessments will be conducted for the enrolled subject as described in the sections below. The Investigator is responsible for ensuring that responsibilities for all assessments are delegated to appropriately qualified site personnel.

7.3.1 Demographics

Age, sex, race, and ethnicity will be collected at the Screening/Baseline visit (D1).

7.3.2 *Medical History/Concomitant Medications*

Fully document concomitant medications (taken within the past 30 days prior to the Screening/Baseline Visit) and Medical History (within 1 year prior to the Screening/Baseline Visit) in the subject source documents (i.e., subject's chart). If the subject reports any condition in Table 3, the Investigator may ask for additional information at their discretion.

AEs are collected from the time of informed consent. Any preexisting medical conditions or signs/symptoms present in a subject prior to the start of the study (i.e., before informed consent is signed) are not considered AEs in the study and should be recorded in the Medical History section of the eCRF.

In the electronic data capture (EDC), only limited information regarding concomitant medications and medical history will be captured, as noted below.

- Medical History: Document all ocular history and targeted systemic history. In the EDC, there is a prepopulated dropdown field with items of interest that is consistent with Table 3.
- Concomitant medications: Document all ocular medications and targeted systemic medications used to treat conditions documented in Medical History and AEs.

Table 3. Targeted Medical History

Medical History	Definition
Active Respiratory Infections	
• Principal respiratory viruses known to cause ocular disease in humans:
○ Adenovirus○ Influenza virus○ Respiratory syncytial virus○ Coronavirus○ Rhinovirus○ Human metapneumovirus
Alcohol Abuse	
• Heavy drinking: current or past consumption of 4 or more servings of alcoholic beverages daily
Atopic Disease	
• Atopy
○ Atopic dermatitis○ Urticaria○ Angioedema○ Asthma○ Allergic rhinitis
Cancer	
• Cancers (potentially metastatic to eye or orbit), e.g., breast and lung cancer for women, gastrointestinal cancer for men, etc.• Cancers on active chemo- or radiotherapy
Diabetes Mellitus	
• All Type I and II, some potential risk factors for retinopathy include:
○ Long duration○ Insulin dependence○ Increased Hemoglobin A1c levels○ Elevated systolic blood pressure

Medical History	Definition
	
 ○ Proteinuria ○ Decreased body mass index (BMI)
Headache	
 ● Confirmed diagnosis (regardless of frequency of attacks) of: 
 ○ Migraine with aura ○ Migraine without aura ○ Tension-type headache ○ Cluster headache ● Headache with symptoms: 
 ○ Systemic symptoms (e.g., fever, weight loss) ○ Neurologic symptoms/signs ○ Onset (sudden) ○ Older age (over 50 years) ○ Prior history (new headache) ○ Secondary illnesses (HIV or history of neoplasia)
Hypertension	
 ● Chronic long-standing hypertension ● Acute severe hypertension
HIV Infection	
 ● Human immunodeficiency virus (HIV) disease with or without highly active antiretroviral therapy (HAART) ● Low CD+ T-cell count (<100 cells /μL) is associated with severe ocular manifestations
Lupus	
 ● Systemic Lupus Erythematosus (SLE) is a chronic, idiopathic, multisystem inflammatory disease characterized by hyperactivity of the immune system and prominent autoantibody production
Multiple Sclerosis	
 ● Multiple sclerosis (MS) is a chronic relapsing and remitting, episodic demyelinating disease of the central nervous system
Rheumatoid Arthritis	
 ● Rheumatoid Arthritis (RA) is a chronic inflammatory autoimmune disease of unknown etiology that affects approximately 1% of the global population
Rosacea	
 ● Rosacea with any subtype below: 
 ○ Erythematо-telangiectatic ○ Papulopustular ○ Phymatous ○ Ocular rosacea
Sarcoidosis	
 ● Sarcoidosis is a systemic inflammatory disease of unknown etiology characterized by the formation of noncaseating granulomas.
Scleroderma	
 ● Systemic sclerosis sine scleroderma is a rare, chronic autoimmune disease with unknown etiology. Its prominent features are fibrosis, vasculopathy, and impaired immune response.
Seronegative spondyloarthropathies	
 ● Ankylosing spondylitis ● Reactive arthritis ● Bechet's disease ● Inflammatory bowel diseases ● Psoriatic arthritis
Sjogren's Syndrome	
 ● Primary Sjogren's syndrome ● Secondary Sjogren's syndrome
Smoking	
 ● Current smoker (regardless of number of pack-years) ● Former smoker (cessation < 20 years before the study)

Medical History	Definition
Systemic Herpes Zoster Infection	
 A viral infection caused by varicella-zoster characterized by painful rash with blisters.
Thyroid Disorder	
 Hyperthyroidism (e.g., Graves' disease) Hypothyroidism (e.g., Hashimoto's thyroiditis) Euthyroid
<Ocular – Other>	[Specify - if not indicated above]

7.3.3 *Efficacy Assessments*

Planned time points for all efficacy assessments are provided in Table 4.

7.3.3.1 IDEEL-SB (Group 1)

Dry eye symptoms will be assessed using the IDEEL-SB questionnaire (see Appendix 17.2.1) at the Screening/Baseline visit (D1), before Systane Ultra PF use, and at Visit 3 (and at unscheduled and at early exit visit, as necessary).

The IDEEL-SB (Version 1) symptom bother module consists of 20 questions that assess general dry eye symptoms a subject experiences. It should be administered prior to performing any other study testing procedure. The subject's response to each question will be entered on paper and scored to determine the eligibility of the subject to participate in the study.

Administration and Scoring

A paper copy of the IDEEL-SB module will be given to each subject for completion without assistance. All questions should be answered by the subject so please check the questionnaire before the subject leaves the study visit.

Question 1 is scored on a 5-point Likert-type scale where 0 = None of the time, 1 = A little of the time, 2 = some of the time, 3 = Most of the time, and 4 = All of the time. Questions 2-20 are scored on a 4-point Likert-type scale where 0 = I did not have this symptom / Not Applicable, 1 = Not at all, 2 = Slightly, 3 = Moderately, 4 = Very much.

The subject will be instructed to select a single response that best represents their answer. The score is calculated if at least 50% (10 items) of the 20 items within the dimension are completed; non-missing; otherwise the score is set to missing. The Symptom Bother score is calculated as the mean value of the non-missing item scores 1-20 multiplied by 25.

[figure not shown]
$$\frac{\text{Sum of responses from questions 1- 20}}{\text{Number of questions (1-20) answered}} \times 25 = \text{IDEEL SB score}$$

The final calculated IDEEL-SB score for each patient will be entered into the study source documents to determine eligibility at the Screening Visit.

7.3.3.2 CLDEQ-8 (Group 2)

CL symptoms will be assessed using the CLDEQ-8 questionnaire (see Appendix 17.2.2) at the Screening/Baseline visit (D1), before Systane Ultra PF use, and at Visit 3 (and at unscheduled and at early exit visit, as necessary).

The final calculated CLDEQ-8 score as the sum of the 8 questions will be entered into the study source documents to determine eligibility at the Screening/Baseline Visit.

7.3.4 *Safety Assessments*

Planned time points for all safety assessments are provided in Table 4.

